3.0 OBJECTIVE(S) & HYPOTHESIS(ES)

3.1 Primary Objective(s) & Hypothesis(es)

- 1) **Objective:** To evaluate the safety and tolerability of single SC doses of MK-1092 in healthy adult subjects. (Parts 1 and 2)
- 2) **Objective:** To evaluate the safety and tolerability of single SC doses of MK-1092 in adult subjects with T1DM and in adult subjects with T2DM. (Part 3 and Part 4)
- 3) **Objective:** To determine the mean GIR_{max} required to maintain target glucose levels in a euglycemic clamp setting of MK-1092 in adult subjects with T1DM following single SC dosing. (Part 3)

Hypothesis:

- 1) At a dose with sufficient safety, the mean GIR_{max} after single SC administration of MK-1092 in adult subjects with T1DM is between 1.5 and 4.5 mg/kg/min. (Part 3)

3.2 Secondary Objective(s) & Hypothesis(es)

- 1) **Objective:** To determine the mean GIR_{max} required to maintain target glucose levels in a euglycemic clamp setting of MK-1092 in healthy adult subjects following single SC dosing. (Part 1)
- 2) **Objective:** To determine the mean GIR_{max} required to maintain target glucose levels in a euglycemic clamp setting of MK-1092 in adult subjects with T2DM following single SC dosing. (Part 4)
- 3) **Objective:** To determine the mean of the time-weighted average based on GIR [TWA(GIR)] required to maintain target glucose levels in a euglycemic clamp setting of MK-1092 in healthy adult subjects, in adult subjects with T1DM, and in adult subjects with T2DM following single SC dosing. (Parts 1, 3, and 4)
- 4) **Objective:** To estimate the plasma PK profile (e.g., C_{max} , $AUC_{0-\infty}$, CL/F , T_{max} , apparent terminal $t_{1/2}$) of MK-1092 after SC dosing in healthy adult subjects, in adult subjects with T1DM, and in adult subjects with T2DM. (Parts 1, 3, and 4)

3.3 Exploratory Objectives

- 1) **Objective:** To explore the levels of serum free fatty acids (non-esterified fatty acids, NEFA) and plasma glycerol after SC dosing of MK-1092 or glargine in healthy adult subjects, in adult subjects with T1DM, and in adult subjects with T2DM. (Parts 1, 2, 3, 4)
- 2) **Objective:** To explore the PK and glycemic effect of addition of IV Humalog infusion following SC dosing of MK-1092 in healthy adult subjects. (Part 2)
- 3) **Objective:** To explore the relationship between genetic variation and response to the treatment(s) administered, and mechanisms of disease. Variation across the human genome may be analyzed for association with clinical data collected in this study.

4.0 BACKGROUND & RATIONALE

4.1 Background

Refer to the Investigator's Brochure (IB) for detailed background information on MK-1092.

4.1.1 Pharmaceutical and Therapeutic Background

Diabetes mellitus (Type 1 and Type 2; T1DM, T2DM) is a global public health issue believed to affect over 400 million individuals worldwide in 2015, and is estimated to affect almost 650 million by 2040 [1]. Currently nearly 10% of the U.S. population is directly affected by the disease, and by 2050 it is estimated that 1 in 3 American adults will have diabetes [2]. According to CDC statistics, 14% of all patients with diabetes in the U.S. are on insulin alone, and another 13% are on a combination of insulin and oral therapy [2]. Basal insulin, which is intended to maintain normal glucose levels during fasting, is the most commonly used form of insulin by patients with T2DM and is used by all patients with T1DM.

Although insulin has been a mainstay of diabetes therapy for decades, exogenously administered insulin poses short-term risks and long-term drawbacks. Excessive basal insulin leads to hypoglycemia, followed by several days of dose adjustment to achieve a new steady-state response. Practitioners and patients thus often settle at moderate under-dosing of basal insulin and/or preemptive ingestion of carbohydrates, such as snacking before exercise or bedtime, to mitigate the risk for hypoglycemia associated with basal insulin. However, these strategies occur at the expense of not achieving target glycemic levels and thereby increasing the risk of long term complications of diabetes.

The goal of the Insulin Receptor Partial Agonist (IRPA) program is to develop a novel, once-daily SC basal insulin with a wide therapeutic index (TI), permitting more aggressive treatment to the glycemic target with reduced risk of hypoglycemia. The improved TI of an IRPA would significantly reduce the risk of hypoglycemia relative to available basal insulins, thus allowing more confidence for practitioners and patients to dose titrate IRPA to attain target goals for control of fasting glucose.

MK-1092 lowers glucose levels effectively but with a flatter dose response curve, an attenuated maximal effect, and extended duration of action in diabetic animal models relative to comparator insulins.

This study will be the first introduction of MK-1092 into human subjects, and will evaluate the safety, tolerability, PK and PD of MK-1092 in healthy adult subjects, adult subjects with T1DM, and adult subjects with T2DM.

4.1.2 Ongoing Clinical Trials

Preliminary Safety and Tolerability

To date, single subcutaneous doses of MK-1092 up to 64 nmol/kg have been evaluated in Part 1 (healthy adult subjects: Panels A [4.0 nmol/kg], B [8.0 nmol/kg], C [16 nmol/kg], D

[32 nmol/kg], and E [64 nmol/kg]); a dose of 8.0 nmol/kg has been evaluated during co-administration with IV Humalog in Part 2 (healthy adult subjects); doses of 8.0 nmol/kg (Panel G) and 32 nmol/kg (Panel H) have been evaluated in Part 3 (subjects with T1DM), and doses of 32 nmol/kg (Period 1) and 16 nmol/kg (Period 2) have been evaluated in Part 4 (subjects with T2DM).

All doses have been safe and well-tolerated. There have been no serious adverse events and no discontinuations due to treatment-emergent adverse events. All adverse events have been mild or moderate and have resolved spontaneously.

There have been no clinically significant changes in vital signs, laboratory parameters, or ECG findings. In Part 1 Panel B (8.0 nmol/kg), three different subjects experienced a mild and transient injection site reaction (injection site pain, injection site pain, injection site tenderness, respectively). In Part 1 Panel C (16 nmol/kg), three different subjects experienced a mild and transient injection site reaction (injection site pain, injection site pain, injection site burning, respectively). In Part 1 Panel E (64 nmol/kg), one subject experienced a mild and transient injection site soreness. In Part 3 Panel H (32 nmol/kg), one subject experienced a mild and transient injection site tenderness. In Part 4 Period 1 (32 nmol/kg), one subject experienced mild and transient pain at the injection site and another subject experienced an upper chest rash due to ECG leads. None of these events were evaluated as being an event of clinical interest (ECI). In Part 3 Panel G (8 nmol/kg), one subject experienced a mild and transient injection site erythema that was reported to the Sponsor as an ECI as well as a separate experience of transient erythema to ECG leads. One other subject in Part 2 Panel F reported an ECI of dermatitis that was deemed unrelated to the study drug by the investigator. No injection site reactions were reported in other panels, including Part 1 Panel A (4 nmol/kg) and Panel D (32 nmol/kg). Treatment allocation (MK-1092 vs glargine) for Part 1, Part 3, and Part 4 remains blinded.

Preliminary Pharmacokinetics

A summary of the observed PK for the MK-1092 4.0 nmol/kg to 64 nmol/kg dose groups in Part 1 and for Part 3 Panel G (8.0 nmol/kg) is provided below. The PK from Part 3 Panel H and from Part 4 (Periods 1 and 2) is pending at the time of amendment 04.

| Preliminary PK Parameters for MK-1092-001 Part 1 (4.0 – 64 nmol/kg) and Part 3 (8.0 nmol/kg) | | | | | | |
|---|-----------------------|---|-----------------------------|-----------------------------|----------------------------------|-------------------------------------|
| | Dose (nmol/kg) | T_{max} (hr)[¶] | t_{1/2} (hr) | C_{max} (nM) | AUC_{0-∞} (nM·hr) | AUC_{0-24hr} (nM·hr) |
| Part 1 | 4.0 | 18 (9.0-18) | 7.00 (31.42) | 0.382 (21.70) | 9.86 (15.37) | 6.43 (20.78) |
| | 8.0 | 12 (4.0-18) | 6.37 (25.85) | 0.747 (25.03) | 17.8 (15.36) | 12.94 (22.49) |
| | 16 | 18 (4.0-24) | 5.47 (27.90) | 1.63 (12.68) | 37.8 (10.09) | 26.03 (21.43) |
| | 32 | 18 (9.0-18) | 5.79 (16.91) | 2.91 (18.73) | 75.8 (10.28) | 48.86 (15.83) |
| | 64 | 12 (12-18) | 9.03 (73.0) | 6.82 (27.6) | 161 (14.1) | 108 (27.1) |
| Part 3 | 8.0 | 15 (9.0-18) | 7.81 (21.6) | 0.788 (20.4) | 22.6 (22.4) | 13.9 (17.8) |
| [¶] Median (Min-Max). All other parameters are expressed as geometric mean (CV). | | | | | | |

Exposures were comparable to predicted values. Following a single dose administration, the geometric mean of apparent terminal half-life ranged ~5.5-9 hr and T_{max} ranged ~12-18 hr at 4.0 nmol/kg to 64 nmol/kg in Part 1. MK-1092 AUC_{0-∞} and C_{max} appeared to be approximately dose proportional. The PK parameters for 8.0 nmol/kg were similar in Part 1 and Part 2 based on preliminary analysis. The PK parameters at 8.0 nmol/kg in Part 3 were comparable to the PK parameters at 8.0 nmol/kg in Part 1.

No anti-drug antibodies (ADAs) or anti-insulin antibodies (AIA) have been detected in Part 1 Panel A-D, Part 2, or Part 3 at up to 28 days after dosing. In Part 1 Panel E, no ADA or AIA have been detected at up to 28 days in 7 of 8 subjects; the 8th subject was lost to follow-up after 14 days and no ADA and AIA had been detected at up to 14 days after dosing for this subject.

Preliminary Pharmacodynamics

A summary of the observed GIR_{max} for the MK-1092 4.0 nmol/kg to 64 nmol/kg dose groups in Part 1 (NHV), for the MK-1092 8.0 nmol/kg and 32 nmol/kg dose group in Part 3 (T1DM), and for the 32 nmol/kg and 16 nmol/kg dose group in Part 4 (T2DM) are provided below. The GIR_{max} for all adult subjects randomized to glargine in any group of Part 1 (Panels A – E), Part 3 (Panel G and H), and Part 4 (Period 1 and 2) are also provided.

| Part 1 GIR_{max} values for MK-1092-001 (4-64 nmol/kg) and Glargine (3.0 nmol/kg), Part 3 GIR_{max} values for MK-1092-001 (8.0 nmol/kg and 32 nmol/kg) and Glargine (3.0 nmol/kg), and Part 4 GIR_{max} values for MK-1092-001 (16 nmol/kg and 32 nmol/kg) and Glargine (3.0 nmol/kg) | | |
|---|---------------------------------|--------------------------------------|
| | Dose | GIR_{max} (mg/kg/min) |
| Part 1 | MK-1092 4.0 nmol/kg | 0.9 |
| | MK-1092 8.0 nmol/kg | 1.7 |
| | MK-1092 16 nmol/kg | 3.1 |
| | MK-1092 32 nmol/kg | 3.3 |
| | MK-1092 64 nmol/kg | 4.4 |
| | Glargine 3.0 nmol/kg (0.5 U/kg) | 2.9 |
| | Part 3 | MK-1092 8.0 nmol/kg |
| MK-1092 32 nmol/kg | | 2.9 |
| Glargine 3.0 nmol/kg (0.5 U/kg) | | 2.5 |
| Part 4 | MK-1092 16 nmol/kg | 1.4 |
| | MK-1092 32 nmol/kg | 1.9 |
| | Glargine 3.0 nmol/kg (0.5 U/kg) | 1.2 |

In Part 1, a dose of 8.0 nmol/kg was safe, well-tolerated, and achieved GIR_{max} of ~1-2 mg/kg/min in healthy adult subjects. Therefore, this dose was tested with Humalog infusion in Part 2 in healthy adult subjects. In Part 2, all healthy subjects achieved GIR_{max} > 4 mg/kg/min. A dose of MK-1092 8.0 nmol/kg was therefore used as the initial dose in Part 3 (adult subjects with T1DM). After 8.0 nmol/kg was tested in Part 2, subsequent panels in Part 1 testing up to 64 nmol/kg have been resumed. A dose of 32 nmol/kg was used as the initial dose in Part 4 (adult subjects with T2DM). A dose of 16 nmol/kg was used as the second dose in Part 4 so as to explore the PD effects of doses below 32 nmol/kg. These doses have been safe and well-tolerated.

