In Part 4, subjects will be blinded in a double-dummy fashion, so that each subject will receive MK-1092/glargine and a matched placebo to the alternative active treatment. Dosing in the first period of this part will use a SC dose no higher than one that has been determined to be safe and tolerated in Part 1. At the time of protocol amendment 03, doses ≤ 64 nmol/kg have fulfilled these criteria. At the time of protocol amendment 04, a dose of 32 nmol/kg was administered in Period 1 and a dose of 16 nmol/kg was administered in Period 2. Dosing in Period 3 of Part 4 will commence upon review of the safety data from previous periods within Part 4 and determination of an acceptable safety profile to continue dose escalation. Up to 3 doses of MK-1092 will be administered in successive periods. The glargine dose will be the same in all periods of Part 4 and is expected to achieve $GIR_{max} \sim 2$ mg/kg/min. The MK-1092 doses will include, and may escalate beyond, the expected therapeutic insulin concentration range for a GIR_{max} of $\sim 1-2$ mg/kg/min. Doses in Part 4 will not exceed 64 nmol/kg SC, which is the highest planned dose in the clinical program. Unlike in Parts 1-3, in Part 4 the same subjects will participate in each period (N=6 receiving MK-1092, N=3 receiving glargine). Subjects in Part 4 who are randomized to MK-1092 in Period 1 will receive MK-1092 in the subsequent periods, and subjects in Part 4 who are randomized to glargine in Period 1 will receive glargine in the subsequent periods. All subjects will complete dosing in Period 1 prior to the start of Period 2, and all subjects will complete dosing in Period 2 prior to the start of Period 3. In addition, determination of an acceptable safety profile in Period 1 will be required prior to starting Period 2 and an acceptable safety profile in Period 2 will be required prior to starting Period 3. At least 7 days will occur between dose administrations in Part 4 to allow for washout. Furthermore, an operational pause will be implemented between Period 2 and Period 3 in Part 4 only to allow sufficient time for analysis of data collected in prior periods of Part 4 and/or panels of Parts 1 and 3 to

inform on dose decisions related to Period 3. The objectives for this part will assess safety and tolerability of the SC injection, PK, and PD endpoints for MK-1092 and glargine in adult subjects with T2DM.

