4.2.3.2 Pharmacokinetic Endpoints

The PK profile of MK-1092 will be assessed in all parts of the trial. Subjects in Parts 1, 3, and 4 will have a single sample collected for glargine or MK-1092 PK, so treatment will remain blinded. Sufficiently sensitive assays for MK-1092 have been developed that will

allow determination of concentrations even at the lower dose levels in this protocol. No urine will be collected for PK.

In Parts 1, 3, and 4, PK assessment will be critical in understanding PD. Specifically, the PD endpoint (GIR_{max} , see below) will be coupled with plasma MK-1092 concentration to determine the concentration–GIR response of MK-1092. Similarly, the PD endpoint of GIR_{max} will also be coupled with glargine concentration for those subjects receiving glargine in Parts 1, 3, and 4. In addition, C_{max} and T_{max} , plasma exposure ($AUC_{0-\infty}$) will also be measured, as will apparent terminal half-life ($t_{1/2}$) reflective of the absorption half-life after SC administration.

In Part 2, PK of MK-1092 will be collected throughout the infusion, similar to as in Part 1 but at slightly different time points to correspond with the timing of Humalog infusion. After Humalog administration, samples will continue to be collected for MK-1092 PK as well as additional samples will be collected for Humalog PK.

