5.2.3 Trial Blinding

Part 2 is open-label; therefore, the Sponsor, investigator and subject will know the treatment administered.

For Parts 1, 3 and 4, a double-blinding technique will be used. MK-1092 and glargine will be prepared and/or dispensed in a blinded fashion by an unblinded pharmacist or qualified trial site personnel. The subject and the investigator who is involved in the treatment or clinical evaluation of the subjects are unaware of the group assignments.

Subjects participating in Parts 1, 3 and 4 will receive injections of MK-1092/glargine and placebo matched to the alternative active treatment (i.e. subjects will receive either MK-1092 and glargine-matched placebo, or glargine and MK-1092-matched placebo).

See Section 7.1.4.2, Subject Blinding/Unblinding, for a description of the method of unblinding a subject during the trial, should such action be warranted.

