- m. Blood for MK-1092 and glargine PK assay will be collected at the following timepoints within Periods 1 and 2: -15 min (predose), 30, 60, 120, 180, 240, 360, 540, 720, 1080, 1440 min, 48 hr, 72 hr, and 96 hr, following start of injection (i.e. - 15 min, 30 min, 1.0 hr, 2.0 hr, 3.0 hr, 4.0 hr, 6.0 hr, 9.0 hr, 12 hr, 18 hr, 24 hr, 2d, 3d, and 4d after SC dose). Blood for MK-1092 and glargine PK assay will be collected at the following timepoints within Period 3 only: -15 min (predose), 60, 180, 240, 360, 540, 720, 1080, 1440 min, 48 hr, and 72 hr, following start of injection (i.e. - 15 min, 1.0 hr, 3.0 hr, 4.0 hr, 6.0 hr, 9.0 hr, 12 hr, 18 hr, 24 hr, 2d, and 3d after SC dose). Blood will also be collected at Post-trial (Day 14 and Day 28 relative to the last period dosed). Exploratory analysis for MK-1092 metabolites may be performed. Any adjustments will be noted in a Protocol Clarification Letter when determined, but the total number of samples will not change. Note that subjects will have only one (1) sample collected for MK-1092 and glargine PK at each time point and this sample will be processed and shipped to the appropriate laboratory for the respective PK assay (MK-1092 PK or glargine PK) by the unblinded lab personnel.
- n. IV infusion of insulin and dextrose, as needed, will begin at the start of the 8 hr overnight fast on Day -1 within each period. IV insulin will be weaned following SC dosing with MK-1092/glargine in order to maintain glucose concentrations at ~100 mg/dL.
- o. Glucose infusion will be discontinued at the discretion of the investigator as detailed in the Study Operations Manual. The duration of the infusion may be shorter or longer than the 24 hr noted above.
- p. Plasma for bedside glucose analysis should be collected at approximately -5 min predose and ~every 1 to 5 min. If necessary, collection may be performed more frequently at investigator's discretion. Bedside glucose analysis will continue at the discretion of the investigator and will be dependent on the duration of the clamp procedure. The duration of bedside glucose analysis may be shorter or longer than the 24 hr noted above. Additional glucose measurements will be assessed using Yellow Springs Instrument (YSI) per the Study Operations Manual and site SOP.

- q. Post-clamp procedures are to be performed shortly after the completion of the clamp (up to +10 min), unless the clamp is concluded within 30 min of a previous collection time.

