7.1.3.2.4 Blood Collection for Blood Glucose (Bedside Analysis)

Ambient glucose concentrations from blood will be recorded frequently (approximately 5 minutes apart) by point-of-care assessment at the bedside per site operating procedures to guide titration of glucose infusions in achieving specified glycemic target levels. Additional glucose measurements will be assessed using Yellow Springs Instrument (YSI) per the Study Operations Manual and site SOP.

Glucose infusion rates will be recorded frequently throughout the infusion/clamp procedure per site standard operating procedures.

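### Does printing Part 4 GIRmax by treatment before Period 3 undermine the blind?

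*Combined protocol and SAP*

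**What the plan says.** The preliminary pharmacodynamics text in section 4.1.2 presents GIRmax "for the 32 nmol/kg and 16 nmol/kg dose group in Part 4 (T2DM) are provided below", and the table splits Part 4 by treatment; one row reads "Part 4 | MK-1092 16 nmol/kg | 1.4". The other two Part 4 rows are 1.9 mg/kg/min for MK-1092 32 nmol/kg and 1.2 for glargine over Periods 1 and 2. The safety text of the same section states: "Treatment allocation (MK-1092 vs glargine) for Part 1, Part 3, and Part 4 remains blinded".

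Part 4 re-doses the same subjects. Section 2.1 plans six on MK-1092 and three on glargine, and says "subjects in Part 4 who are randomized to glargine in Period 1 will receive glargine in the subsequent periods". Period 3 is still ahead at amendment 04. Section 5.2.3 defines the blind for Parts 1, 3 and 4: "The subject and the investigator who is involved in the treatment or clinical evaluation of the subjects are unaware of the group assignments". The sponsor is not named there as blinded.

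The site runs the clamp: "Glucose infusion rates will be recorded frequently throughout the infusion/clamp procedure per site standard operating procedures" (section 7.1.3.2.4). The plan also takes care over drug assays. Section 4.2.3.2 says "Subjects in Parts 1, 3, and 4 will have a single sample collected for glargine or MK-1092 PK, so treatment will remain blinded", and footnote m of the Part 4 flow chart has samples sent "for the respective PK assay (MK-1092 PK or glargine PK) by the unblinded lab personnel".

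**The concern.** The investigator signs and works from this protocol (section 10.3) and also holds each subject's infusion rates from Periods 1 and 2. With nine subjects split 6 and 3, there are only 84 possible allocations. Someone could look for the split whose averages match 1.9, 1.4 and 1.2 and carry the result into Period 3. Part 4 is the only part where this can arise, because subjects in Parts 1 and 3 enter one panel only. It also sits oddly beside the precautions taken with the pharmacokinetic samples.

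If the arms could be inferred, two judgements in Period 3 would be exposed: the investigator's causality assessment of adverse events (section 7.2.4) and the discretion to end a clamp early (section 4.2.2.4).

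**Working it through.** **Is a stated rule broken?** Section 5.2.3 keeps the subject and investigator unaware of group assignments. The section 4.1.2 table gives one value per treatment and no subject's code, so the statement that allocation remains blinded is true at subject level. Feeding pharmacodynamic results by dose into decisions is part of the design: Part 2 could start only once a Part 1 dose had reached GIRmax of about 1-2 mg/kg/min, and that dose was communicated to the site (section 2.1).

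**How much does the table add?** The plan has no figure on this, so it was simulated.

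Inputs from the documents:
- Means 1.9 and 1.4 (MK-1092) and 1.2 (glargine, both periods pooled), from section 4.1.2.
- Six and three subjects, from section 2.1.
- SD 0.44, from section 8.8. It is the only GIRmax SD given, and comes from another IRPA in healthy subjects.

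Assumptions:
- Normal values and within-subject correlation 0.5.
- Printed values are arithmetic means rounded to 0.1.
- Larger SDs of 0.8 and 1.2, because no T2DM SD is documented.
- Read error: the SD of the difference between the maximum the site reads and the sponsor's LOESS-smoothed maximum.

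Method: 20,000 datasets per setting. Number of allocations = C(9,3) = 84. With the table, choose the allocation whose three averages lie closest to the printed values. Without it, call the three subjects with the lowest Period 1 GIRmax glargine; section 4.2.3.3 already tells the reader that MK-1092 may run higher. Pure chance would label (6/9)² + (3/9)² = 55.6% correctly.

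Subjects labelled correctly, with table vs without:

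| SD | error 0 | error 0.1 | error 0.2 | error 0.3 |
|---|---|---|---|---|
| 0.44 | 88.9 vs 81.5% | 83.5 vs 81.0% | 77.6 vs 79.3% | 73.4 vs 77.6% |
| 0.8 | 88.9 vs 70.8% | 81.9 vs 70.4% | 75.4 vs 70.1% | 71.8 vs 69.6% |
| 1.2 | 92.1 vs 65.6% | 85.0 vs 65.5% | 77.1 vs 65.3% | 72.9 vs 65.1% |

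At SD 0.44 the gain is 88.9 − 81.5 = 7.4 points at error 0, 2.5 at 0.1, then −1.7 and −4.2. Most of what can be inferred comes from the infusion rates themselves, which no edit to the protocol removes.

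**Sensitivity to the printed statistic.** The GIRmax table does not say what it prints; the neighbouring PK table gives geometric means for all parameters except Tmax. For a reader who matches arithmetic means at read error 0 (values floored at 0.05):

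| Printed as | SD 0.44 | SD 0.8 | SD 1.2 |
|---|---|---|---|
| geometric mean | 85.9 vs 81.7% | 74.5 vs 70.5% | 68.8 vs 65.2% |
| median | 78.4 vs 81.3% | 70.9 vs 70.3% | 68.8 vs 65.5% |

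The gains at SD 0.8 and 1.2, which were 18.1 and 26.5 points, fall to between 0.6 and 4.0.

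**Sensitivity to a missing subject.** Section 8.5 allows exclusions. With one MK-1092 subject left out of the printed values and read error 0, the gain is 0.2, 3.7 and 5.9 points at SD 0.44, 0.8 and 1.2. With one glargine subject left out it is −1.5, 3.0 and 5.9.

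**Sensitivity to the no-table guess.** The site knows that the MK-1092 dose went from 32 to 16 nmol/kg while glargine stayed fixed. At SD 0.44 and correlation 0.8, ranking on Period 1 minus 0.4 × Period 2 gives 86.3% without the table against 90.8% with it at error 0, and 85.0% against 85.0% at error 0.1. At correlation 0.5 this ranking changes little.

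**What does the disclosure serve?** No escalation happens without the investigator's agreement, and pharmacodynamic data may enter that decision (section 5.2.1.2). The top dose may be withheld if pharmacodynamic targets are already met (section 4.2.2.3). The pause before Period 3 exists so that earlier data can inform its dose (section 2.1). A value pooled over six MK-1092 and three glargine subjects could not show whether MK-1092 had reached its target.

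**The case for a change.** The strongest reply is that closest match is a crude rule, so its losses at larger read errors are an artefact. That is right. An ideal observer, who weighs all 84 allocations and knows the true means, SD and correlation with or without the table, always gains. At SD 0.44 the figures are 90.5 vs 82.3%, 86.7 vs 81.6%, 83.1 vs 80.2% and 79.7 vs 77.8% at errors 0, 0.1, 0.2 and 0.3. The gain runs from 8.2 points down to 1.9, that is 9 × 0.082 = 0.7 to 9 × 0.019 = 0.2 of the nine subjects.

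Subjects with T2DM may also vary more than 0.44. If so, if the printed values are arithmetic means, and if the site reads the maxima almost exactly, the gain is 11.5 to 26.5 points at read errors up to 0.1. Exactly one allocation then fits and is correct in 45 to 64% of datasets at error 0 (SD 0.44 to 1.2), 13 to 20% at 0.1, and 2% at 0.3. This stands as a possibility, but the documents establish none of the three conditions. The LOESS span is not stated, so the size of the read error is unknown.

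It is also fair that Part 4 safety is a primary objective and rests on the investigator's judgement. But the route to harm is thin. Safety is summarised descriptively, Part 4 has no formal GIR hypothesis (section 8.1), and the clamp has an objective end rule alongside the discretion. The definition of the sponsor's product in section 7.2 can extend to an active comparator, so a guess at the arm need not change a causality answer.

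**Conclusion.** The concern does not hold. The table is in the protocol and Period 3 is still to come, but no assignment is disclosed and no statement in the plan is contradicted. At the one documented SD, closest match gains about 7 points if the site reproduces the sponsor's maxima exactly, 2 to 3 points at a read error of 0.1, and nothing from 0.2; an ideal observer gains 8 points falling to 2. Larger gains need a higher SD together with near-exact reading and an arithmetic mean, none of which is documented. All these figures rest on assumed normality and within-subject correlation.

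Against that uncertain gain, withholding the arm split would deprive an investigator who must jointly agree the Period 3 dose of relevant data. Printing it is a defensible trade-off. No effect on the Part 3 primary conclusion is shown, since later Part 3 panels use different subjects. Saying in section 4.1.2 that it is subject-level allocation that remains blinded would be a clarification only and would change no result.
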